Outcomes, products and deliverables: Outcomes: The primary treatment outcome will be percent heavy drinking days of alcohol per week. The secondary outcome will be TBI symptom severity as measured by the Neurobehavioral Symptom Inventory (NSI). The exploratory outcomes will be levels of executive functioning (impulsivity, risk-taking, and decision making) and other neurocognitive domains assessed over the course of the study. *Products:* Data will be collected on 8 weeks of treatment plus week 12 follow-up. *Deliverables:*

This study is being sponsored by the Department of Defense (DOD) Telemedicine and Advanced Technology Research Center (TATRC).

II. RESEARCH PLAN

A. GOALS AND SPECIFIC AIMS

The overall goal of the project is to improve the care of veterans with traumatic brain injury and unhealthy alcohol use. We will conduct a pilot controlled clinical trial to assess the efficacy of N-acetylcysteine (NAC) to reduce alcohol use and improve brain injury symptoms in veterans with TBI who consume alcohol at *hazardous or harmful* levels. This project builds upon our current ITN-funded research on topiramate pharmacotherapy for unhealthy alcohol use in veterans with TBI.

A.1. PRIMARY AIMS:

Aims:

Measure both alcohol use and TBI symptom severity over the course of the 12-week study in order to detect differential efficacy of NAC and placebo. Alcohol use treatment outcome will be the Percent Days of Heavy Drinking (PHDD) of alcohol

A heavy drinking day is defined using NIAAA (2007) criteria: any day with 5 or more drinks per day for men or 4 or more drinks per day for women⁸. The choice of PHDD as the primary outcome is based on its endorsement by a recent NIAAA consensus conference⁹ and its increasing use in clinical trials ¹⁰⁻¹². TBI symptom severity will be measured with the Neurobehavioral Symptoms Inventory (NSI)^{13,14} a measure of postconcussive symptom severity.

Hypotheses:

Our **two primary** aims examine group differences, to detect differential efficacy of NAC vs placebo (*between-group analyses*). We will test the following hypotheses with between-groups analyses:

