We will recruit 30 participants from the San Francisco Veterans Affairs Medical Center (SFVAMC). Recruitment will be through direct outreach to patients via notices and cards in patient areas and asking clinicians to refer patients. Research staff will conduct brief pre-screening to assess possible eligibility. At the SFVAMC, sites will include the Primary Care, Neurology, TBI, Mental Health and Substance Abuse clinics, and affiliated satellite clinics (Community-Based Outpatient Clinics [CBOCs] in Downtown San Francisco, Santa Rosa, CA, and San Bruno, CA), regional Vet Centers and mental health clinics. The Investigator and Research Coordinators will work with staff in outpatient units at the SF VAMC to explain the study, including eligibility criteria, potential risks and benefits to study involvement, how to refer a potential study candidate and how prospective participants can contact study staff. Once a prospective participant has been identified, research staff will conduct a brief telephone or in-person pre-screening interview to assess possible eligibility. If pre-screening is successful, research staff will obtain written informed consent and gather demographic and locator information including contact information for the patient's treatment providers. Written permission will be obtained for research staff to review mental health records and consult with the participant's primary care provider, psychiatrist, and other clinicians to obtain clinical information to assist in the assessments of medical status, psychiatric diagnoses, and substance use. The participant's primary care and/or mental health providers will also be asked for their assent to any patient entering the study.

This study will actively recruit women as participants. Specifically, non-pregnant females, ages 18 to 69, will be eligible to participate. Pregnant females will be excluded from the study because NAC's effects on the developing fetus is unknown and it is not known whether NAC is excreted in human milk.

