Prospective participants will undergo a brief CPRS pre-screen (**see CPRS Screen**) and an in-person or telephone pre-screen (**see Phone Screen**) to establish that they are: 18-69 years of age, screen positive for TBI, drink at hazardous or harmful levels by NIAAA criteria⁸ and wish to reduce or stop alcohol use.

D.3.d. Consent

Breath Alcohol Test Prior to Consent

If the breath alcohol test reading is greater than 0.00%, the participant will be asked to return later that day, or on another day, to be retested.

Consenting

After passing the pre-screen, participants will provide written informed consent in compliance with IRB

PI: [name] regulations. During the consent process, Veterans are asked to abstain from driving to study visits while intoxicated. They are informed that if they do drive and their breath alcohol level is above 0.08, then a clinician will assess their safety before they are allowed to leave the SF VA Medical Center.

D.3.e. Screening

After consent, participants will be scheduled for screening assessments. The screening phase is accomplished over a total of approximately three to four visits extending over one week.

D.3.f. Random Assignment

Participants will be randomly assigned, sequentially as they qualify for the study, to either NAC or placebo in a 1:1 ratio per a computer-generated list provided by a biostatistician. Randomization will be balanced using permuted blocks. Participants and investigators will be blinded to assignment. To maintain the blind, sealed envelopes containing the study drug identification (e.g. NAC or placebo) will be kept together, in a limited access area (the study pharmacist's office) that will be available to the investigators should the blind need to be broken for any individual participant.

D.3.g. Pharmacotherapy

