The *Primary* hypotheses are that NAC treatment will be more efficacious than placebo in reducing PHDDs and TBI symptom severity (NSI). Data analytic technique: *Percent Heavy Drinking Days (PHDD):* Negative binomial regression accommodates over dispersion and derives as an alternative to Poisson regression (most natural for analyzing count data). Heavy percent drinking days is often over-dispersed, positively skewed count data. Therefore, we will use random-intercept zero-inflated negative binomial model, modeling week (week 1 - week 8) as a continuous variable to analyze group differences in PHDD. *Neurobehavioral Symptom Inventory (NSI):* We will use random-intercept linear mixed models to explore the efficacy for NAC related reduction in TBI symptom severity measured by the NSI. Time period will be treated as a repeated effect, with correlations between time periods within participants modeled by an unstructured correlation matrix where appropriate. Model assumptions will be tested and required modifications will be performed. Both models will included fixed effect for week, treatment group (NAC and placebo), and the interaction between treatment group and week. Baseline alcohol consumption and NSI means will be used as respective covariates in group comparisons to control for pre-study and study enrollment effects.

Exploratory Outcomes

Our exploratory hypotheses are that NAC treatment will be more efficacious than placebo in reducing other measures of alcohol use, producing significant improvement in cognitive performance (see section H.4.e), and will be moderated by rs6465084. Data analytic technique: Exploratory hypotheses will be analyzed in a parallel fashion, with separate negative binomial models applied to non-normally distributed count data and mixed linear models used for the remaining normally distributed outcome measures. Assumptions of each model will be tested and any required modifications will be performed. To investigate the potential moderating effect of rs6465084, we will use linear mixed models crossing treatment group with a two-level genotype group (A-allele vs. non A-allele carriers)^{110,121}, looking for a treatment group-by-genotype interaction on PHDD, and other secondary exploratory outcome measures of alcohol use.

Multiple Comparisons

Adjustment for multiple comparisons will be made for the separate families of primary outcomes (PHDD, NSI, cognitive performance) using a modified Bonferroni method¹⁶⁹.

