Estimates of NAC vs placebo for a larger study of HHAU and TBI.

We plan to derive a reliable estimate of effect for planning a large RCT from this small controlled pilot study. It will be useful to obtain estimates of variability in order to inform future controlled trials of NAC treatment for alcohol use. Our sample of n=30, with power of .80 will have the ability to detect an effect size of approximately .65 (one-tailed, alpha = .05). This is conventionally considered a medium effect size. To test for efficacy, we plan to implement intent-to-treat analyses, therefore including all participants randomized to trial. To examine estimates of harm, we will complete Per-Protocol analyses using data from participants exposed to study medications.

Study Limitations/Potential Problems.

Veterans Alcohol TBI PI: [name]

Recruitment, retention, missing data, and safety issues have been the most difficult hurdles facing clinical trials in AUDs. We believe that our research team is demonstrating a high level of success in recruiting (See Table 5) and retaining similar participants with TBI and HHAU, with 81% of participants completing the PI's pilot trial of TOP, a medication with a much higher adverse event profile¹²⁹. Similarly, there has been little missing data, with 81% of weekly study visits attended. Moreover, the use of a mixed-effects model allows for all available data in model estimation. Finally, human participant safety, although a prime concern, is relatively low in the use of NAC¹⁷⁰ (See Human Subjects Section)

I I. Da	[name]			
Table 5. Pl's current trial of				
topiramate in HHAU and mTBI				
Prescreened 255				
Screened (Signed Consent)	25			
Randomized	17 (53%)			
Percent Visits Attended	80.88%			
Percent Attended Week 12	81.25%			

D.3.j. Phlebotomy and Urine Drug Testing

Phlebotomy will be performed at screening, week 4, 8, and 12. Urine drug testing will be performed at screening, week 4, week 8, and week 12.

D.3.k. Participant Payment

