The study will be stopped if, in the judgment of the DSMB or the PI, there are sufficient safety concerns that arise during the conduct of the study that would indicate that participants are being harmed by study interventions. Examples of such safety concerns would be:

- If, after the first 10 participants (33% of the planned enrollment) have completed their study treatment, the interim analysis reveals that more than 50% (i.e. 6 participants) have worsened to a clinically significant degree in the primary outcome measure of alcohol use from baseline to study end.
- Other events that pose unacceptable risks to participants, e.g., multiple SAEs that are judged to be related to study interventions

E.2.h. Rules for Withdrawing Study Participants from the Study Interventions

Participants will be withdrawn from the study if, in the opinion of the DSMB or the PI, there is: sustained clinically significant worsening in the primary outcome measure of alcohol use, unacceptable adverse events judged to be related to study interventions, or any other clinically significant medical, psychiatric, or substance use related poor outcome that makes continued study participation unsafe in the clinical judgment of the PI or DSMB members.

E.2.i. Rules for Breaking the Blind

The blind will be broken for an individual in the study if, in the opinion of the PI or DSMB, there is an emergent clinical need to determine whether a participant is receiving NAC or placebo.

E.3. BENEFITS TO TAKING PART IN THE STUDY

Participants may benefit from the extra physical examination, laboratory tests, and attention to and treatment

PI: [name] of alcohol use disorders. In the informed consent form, participants are instructed: "Taking part in this study may or may not make your health better. If you are in this study, you may benefit from the physical examinations, blood tests, and review of your symptoms. You may respond favorably to the treatment and reduce your drinking and brain injury symptoms, but there is no guarantee that this will happen. Others may benefit from the overall conclusions drawn from the results of this study."

E.4. IMPORTANCE OF THE KNOWLEDGE TO BE GAINED

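### The stated power (30 participants, 80%, effect size about .65) does not follow from its inputs: an unadjusted comparison of 15 per arm detects d = 0.93 and has 54% power at 0.65

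*Combined protocol and SAP*

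**What the plan says.** The only power statement for NAC against placebo is in D.3.i, under the heading on estimates for a larger study: "Our sample of n=30, with power of .80 will have the ability to detect an effect size of approximately .65 (one-tailed, alpha = .05". The next sentence labels this a medium effect. No test, effect-size scale, correlation or dropout allowance is given.

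The rest of the protocol settles what 30 means:

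- D.2.a: "We will recruit 30 participants from the San Francisco Veterans Affairs Medical Center (SFVAMC".
- E.2.g, the stopping rule: "If, after the first 10 participants (33% of the planned enrollment) have completed their study treatment", which again gives a total of 30.
- D.3.f: participants are assigned "to either NAC or placebo in a 1:1 ratio", so 15 per arm.
- A.1: "We will test the following hypotheses with between-groups analyses".

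The planned models (D.3.i, Primary Outcome) are richer than a t-test. For percent heavy drinking days (PHDD) the plan is a random-intercept zero-inflated negative binomial model, "modeling week (week 1 - week 8) as a continuous variable". For the Neurobehavioral Symptom Inventory (NSI) it is a linear mixed model. Both include a treatment-by-week interaction, and "Baseline alcohol consumption and NSI means will be used as respective covariates in group comparisons". No correlation or expected variance reduction is given.

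The other power text, D.6.a.3, concerns a topiramate arm of 16, a within-subjects d of 0.9, and percent drinking days.

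**The concern.** With 15 per arm, 80% power at a standardized difference of 0.65 is implausible for a simple two-group test, even one-sided. The sentence mentions no gain from covariates or repeated measures that would close the gap.

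What is at stake is how a null result is read. Someone who accepts 80% power at .65 would take a null result as evidence against an effect of that size. Section A.3 makes the larger trial conditional on a positive pilot, so that reading matters, although the stated planning use of the pilot is to estimate effect and variability.

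**Working it through.** **Inputs.** Total 30 (D.2.a, E.2.g); 1:1 allocation (D.3.f), so n = 15 per arm; one-sided alpha 0.05, power 0.80 and effect size 0.65 (D.3.i). The t-test is the reader's choice, because the plan names none.

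**Method.** Noncentral t. For two groups of n, the degrees of freedom are 2n − 2 and the noncentrality is d·√(n/2). For a paired test of n people they are n − 1 and d·√n. Power is the probability of exceeding the one-sided 5% critical value.

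**Trying to reproduce .65.**

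| Design, one-sided 0.05 | d at 80% power | Power at 0.65 |
|---|---|---|
| Two groups, 15 per arm (as planned) | 0.931 | 53.7% |
| Two groups, 30 per arm (60 in total) | 0.650 | 80.0% |
| Paired, 16 people | 0.652 | 79.8% |

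For the first row the critical value is 1.701 on 28 df and the noncentrality at 0.65 is 0.65 × √7.5 = 1.780, barely above it, so power is only a little over one half. The normal approximation agrees: detectable d is 0.91 and power is 55%. The other two rows give .65 but do not describe a between-group test of 30 people. The paired n of 16 matches the sample size in D.6.a.3, but that text states d = 0.9, so it is not a source for .65 either.

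**What the planned features could deliver.** Assumptions, none of them in the documents: linear model, equal correlation r among all visits including baseline, no missing data, d in SDs of a single visit, and the tested effect averaged over k post-baseline visits. With D = 0.931:

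- without baseline: D·√[(1 + (k−1)r)/k]
- with baseline: D·√[(1 + (k−1)r)/k − r²]

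| | r = 0.3 | r = 0.5 | r = 0.7 | Maximum over r |
|---|---|---|---|---|
| PHDD, k = 8, no baseline | 0.579 | 0.698 | 0.799 | – |
| PHDD, k = 8, with baseline | 0.508 | 0.520 | 0.463 | 0.524 (r ≈ 0.44) |
| NSI, k = 3, no baseline | 0.680 | 0.760 | 0.832 | – |
| NSI, k = 3, with baseline | 0.620 | 0.601 | 0.518 | 0.620 (r ≈ 0.33) |

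The NSI visits are weeks 4, 8 and 12 (D.4.e.1). A single endpoint adjusted for baseline reaches 0.65 only at a baseline correlation of about 0.72.

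If the tested effect is instead the linear treatment-by-week interaction for PHDD, the detectable difference in change from week 1 to week 8 is 7·D·√[(1 − r)/42], where 42 is the sum of squared deviations of weeks 1 to 8 about their mean. This gives 0.84, 0.71 and 0.55 single-visit SDs at r = 0.3, 0.5 and 0.7.

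All of these are linear approximations, not the power of the zero-inflated negative binomial model.

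**Attrition.** D.3.i cites the earlier topiramate pilot, "with 81% of participants completing". If only completers counted, 0.81 × 15 ≈ 12 per arm, the unadjusted detectable d would be 1.05 and power at 0.65 would be 46%. With baseline adjustment the maxima would be 0.59 (PHDD) and 0.70 (NSI). This is pessimistic, because the mixed models use all available data.

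**The case against.** The strongest reply is that the sentence is under-specified rather than miscalculated. It names no test, so the unadjusted t-test is imported, and nobody plans to run it. The models that are planned adjust for baseline and use repeated measures. On the averaged-effect assumptions above they detect at most 0.52 for PHDD and 0.62 for NSI, so .65 could even be conservative. Also, 30 per arm and a paired test of 16 are not the only routes to .65. At 15 per arm it also follows from a baseline correlation of about 0.72 at one visit, or from unadjusted means over eight visits at r of about 0.41 or three visits at about 0.23.

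Much of this stands. The planned analysis may well have 80% power at 0.65, and the documents do not establish where the figure came from. But every one of these routes needs a correlation, an SD scale and a choice of tested effect that the plan does not state. The results move to either side of .65 as those choices change: the interaction reading runs from 0.84 down to 0.55. One unexplained value for two outcomes with different models and visit counts cannot be checked, and the plainest reading of its stated inputs contradicts it. The sentence also spends the full .05, although the plan commits to a modified Bonferroni adjustment across families of primary outcomes.

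**Conclusion.** The concern holds. As a plain comparison of 15 against 15 at one-sided 0.05, the detectable effect is 0.93 rather than .65, and power at 0.65 is 54% rather than 80%. An unadjusted test with 80% power at 0.65 would need 60 participants, twice the planned total. The documents give no other basis for .65, and D.6.a.3 does not supply one.

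These figures rest only on the documents' total, allocation ratio, sidedness and alpha, plus the choice of an unadjusted t-test as reference. They are not a statement of the planned models' power, which cannot be determined without the missing correlations and scale. The sentence should be fixed because it is the only NAC-versus-placebo power claim. Sample size, analysis and conduct are unaffected.

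**What to change.** Replace the sentence in D.3.i by one of the following.

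1. If .65 (or less) is to stand as the trial's detectable effect, state the test and the tested effect, the assumed baseline and within-person correlations, and the SD scale. Do this separately for PHDD and NSI, and say that a linear calculation only approximates the zero-inflated negative binomial model.
2. Otherwise, give the reference calculation: *30 participants (15 per arm); as an unadjusted reference, a two-sample t-test at one-sided 0.05 has 80% power for d of about 0.93 and about 54% power for d = 0.65, with no allowance for attrition or multiplicity.*

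Keep the medium-effect label only under option 1. In both cases reconcile the sentence with D.6.a.3, whose topiramate arm of 16, within-subjects effect and percent-drinking-days outcome do not describe the NAC-versus-placebo comparison.

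The cost is wording only: no extra participants and no change to the analysis or conduct.

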Percent Heavy Drinking Days (PHDD): Negative binomial regression accommodates over dispersion and derives as an alternative to Poisson regression (most natural for analyzing count data). Heavy percent drinking days is often over-dispersed, positively skewed count data. Therefore, we will use random-intercept zero-inflated negative binomial model, modeling week (week 1 - week 8) as a continuous variable to analyze group differences in PHDD. *Neurobehavioral Symptom Inventory (NSI):* We will use random-intercept linear mixed models to explore the efficacy for NAC related reduction in TBI symptom severity measured by the NSI. Time period will be treated as a repeated effect, with correlations between time periods within participants modeled by an unstructured correlation matrix where appropriate. Model assumptions will be tested and required modifications will be performed. Both models will included fixed effect for week, treatment group (NAC and placebo), and the interaction between treatment group and week. Baseline alcohol consumption and NSI means will be used as respective covariates in group comparisons to control for pre-study and study enrollment effects.

3) Power Analyses for the Primary Outcome

We conducted a power analysis on our current pilot study of topiramate treatment of *alcohol dependence* in veterans with PTSD (see Section C.2.b.). For the outcome measure of percent drinking days (PDD), the effect size from the pilot data comparing week 12 to baseline within the topiramate group is d = 1.87. Because the proposed project is focused on veterans with TBI who have *hazardous* as well as harmful alcohol use, rather than just harmful use (alcohol dependence), we assume that the participants may start at a lower baseline level of DD in the proposed study than in the pilot study. This may not allow us to show as much improvement in the proposed study as in the completed pilot study of PTSD and alcohol dependence. Therefore, it would seem reasonable to target an effect size approximately half of what we found in our pilot study, i.e. d=0.9. A sample size of 16 for the topiramate arm of our proposed placebo-controlled pilot will allow us to detect a within-subjects effect size of d = 0.9, with 80% power at alpha = .05.

D.6.b. Exploratory outcomes/exploratory hypotheses

1) Exploratory Hypotheses

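### The plan fixes no significance level or side for its two primary tests, and its 80% power for an effect of .65 is quoted at an unadjusted one-tailed .05, where 30 participants do not reach it

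*Combined protocol and SAP*

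**What the plan says.** A.1 makes both primary aims between-group comparisons of NAC with placebo: percent heavy drinking days (PHDD) and the Neurobehavioral Symptom Inventory (NSI). D.3.f allocates participants 1:1.

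Four places bear on the significance level:

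- **D.3.i, estimates for a larger study.** For 30 participants and 80% power, the plan gives as its target an "effect size of approximately .65 (one-tailed, alpha = .05". This is the only between-group power statement and the only place where a side is given.
- **D.6.a 3), power analyses.** Here 16 participants in what is called the topiramate arm are said to suffice for a "within-subjects effect size of d = 0.9, with 80% power at alpha = .05". No side is given. The quantity is a within-subjects change in one arm, taken from an earlier topiramate pilot.
- **D.3.i, Multiple Comparisons.** The plan makes this promise: "Adjustment for multiple comparisons will be made for the separate families of primary outcomes (PHDD, NSI, cognitive performance) using a modified Bonferroni method". The text does not name the variant or say how many tests share the level.
- **D.3.i, Primary Outcome, and D.6.a 2).** These describe the models: a random-intercept zero-inflated negative binomial model for PHDD and a linear mixed model for NSI, each with a baseline covariate. They give no level and no side.

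**The concern.** A power figure means something only at the level at which the result will be judged. Here that level is never set. The one between-group figure is quoted at one-tailed .05 with no adjustment, although the same section promises an adjustment over the primary outcomes.

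Two things are at stake. First, a borderline result could be reported as positive or not, depending on a level chosen at analysis. A.3 makes the request for a larger trial depend on positive results, so the definition of positive matters. Second, readers of the power statement will think the trial is more sensitive than it is.

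**Working it through.** **Inputs.** Total 30, power .80, effect .65 and one-tailed .05 (D.3.i); 1:1 allocation (D.3.f), so n = 15 per arm and 28 degrees of freedom; 16 in one arm and d = 0.9 (D.6.a 3)). No dropout is included. D.3.i names no test, so a two-sample t-test with SD 1 serves as an illustration.

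**Formulas.** Noncentrality = d × √(n/2). Power = P(T > critical t), where T is noncentral t with 28 df. Smallest observed d that is significant = critical t × √(2/n), with √(2/15) = 0.365.

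**Step 1: the plan's own figure.** Noncentrality = .65 × √7.5 = 1.780. The critical t at one-tailed .05 is 1.701. Power is 53.7% (normal approximation: Φ(1.780 − 1.645) = 55.4%), not 80%. The d detectable with 80% power is 0.93 (normal approximation: (1.645 + 0.842) × 0.365 = 0.91), not .65.

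**Step 2: where .65 does come out.** At one-tailed .05, d = .65 gives 80.0% with 30 *per arm*. It gives 79.8% in a one-sample (paired) test with n = 16, and 77.3% with n = 15 (80.9% by normal approximation). None of these is a comparison of two arms of 15.

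**Step 3: the D.6.a 3) figure.** A paired test with n = 16 and d = 0.9 gives 96.3% power (one-sided .05) or 91.9% (two-sided .05), not 80%. A *two-sample* one-sided test with 16 per arm gives 80.0%; its two-sided version gives 69.3%.

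**Step 4: the same design at other levels (15 per arm).**

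| Level | Critical t | Smallest significant observed d | Power at d = .65 | d detectable with 80% |
|---|---|---|---|---|
| One-tailed .05 | 1.701 | 0.62 | 53.7% | 0.93 |
| Two-sided .05, or one-sided .025 | 2.048 | 0.75 | 40.5% | 1.06 |
| Two-sided .025 (two-sided .05 split over two) | 2.368 | 0.86 | 29.4% | 1.18 |

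The third row assumes plain Bonferroni over PHDD and NSI. If one-tailed .05 were split over two instead, the level would be one-sided .025, which is the second row.

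**Step 5: a borderline result.** An observed d equal to the plan's .65 gives t = 1.78, above 1.701 and below 2.048. It is positive at one-tailed .05 and negative at two-sided .05, as is any observed d between about 0.62 and 0.75.

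**Step 6: could the baseline covariate rescue the 80%?** At one-tailed .05 the residual variance would have to fall to (.65/0.931)² = 0.488 of the unadjusted variance. With 1 − r² = 0.488, the baseline correlation r would be about 0.72 (about 0.70 by normal approximation). The documents state no such correlation.

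**The case against.** The strongest reply is that D.3.i and D.6.a 3) are power statements and not decision rules, and that they do not conflict. D.6.a 3) concerns a different quantity and is silent on side, and silence does not contradict one-tailed. That stands. A reader might infer that the plan contains competing rules that give opposite verdicts on the same result. The documents do not support this, because no passage says two-sided and none sets a decision rule at all. The defect is an omission. Nor is the direction left open: the hypotheses state in advance that NAC will be better.

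Steps 2 and 3 also suggest, without proving it, that both 80% figures were computed at one-sided .05 under a layout other than the one described. If so, the error lies in the n or the design behind the figure. The stated figure is still wrong for this trial.

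The multiplicity sentence refers to separate families. It can be read as adjusting only within each family, which would leave PHDD and NSI, one measure each, at the full level. The split levels are therefore assumptions. A reader might go further and let an observed d anywhere up to 0.93 change verdict. That needs a side the plan never states and a three-way plain Bonferroni split that counts cognition as primary, although A.2 and D.6.b treat it as exploratory.

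A reader might also take the stopping example in E.2.g as an argument against a one-tailed test. It counts participants who worsened from baseline among the first ten to complete treatment. It is not a comparison between arms, so the side of the primary test does not bear on it.

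Finally, the t-test is not the planned analysis, and this is a pilot meant to inform a larger trial. Both are fair. The d values are illustrative, and a significance verdict matters less here than in a confirmatory trial. The plan nevertheless states efficacy hypotheses, a power claim and a multiplicity adjustment.

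**Conclusion.** The point holds as a gap and an overstated figure. The level and side of the primary tests are never fixed, and the power is quoted at an unadjusted one-tailed .05, the most lenient level the text allows. Even there, two arms of 15 give about 54% power at d = .65 and need d = 0.93 for 80%. At two-sided .05 the figures are about 40% and 1.06. The further fall to about 29% and 1.18 rests on an equal split over two primaries.

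All of this assumes an unadjusted t-test with all 30 participants contributing. Dropout would lower the power. A strong baseline correlation would raise it, but to reach 80% at one-tailed .05 that correlation would have to be about 0.7, which the plan does not claim.

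**What to change.** - In D.6.a 2) and in the statistical plan within D.3.i, state one decision level and side for both primary tests: two-sided .05 overall or, equivalently for efficacy, one-sided .025.
- In the Multiple Comparisons paragraph, say whether PHDD and NSI share that level, and name the variant and the tests it covers.
- In D.3.i, replace the .65 with the effect detectable with 80% power at the chosen level: about 1.06 at two-sided .05, or about 1.18 if it is shared equally over two. If one-tailed .05 is kept unadjusted, the figure is 0.93.
- If the planned mixed models are thought to do better, state the assumed baseline correlation and show the calculation.

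The cost is wording and a less favourable stated figure. Neither sample size nor conduct changes.
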